5.3.3 Concomitant medication date imputation

Impute concomitant medication (CM) end date:

1. If CM end day is missing and CM month/year are non-missing then impute CM day as the minimum of treatment end date and the last day of the month.
2. If CM end day/month are missing and CM year is non-missing then impute CM day as the minimum of treatment end date and the end of the year (31DECYYYY).
3. If imputed CM end date is less than the CM start date, use the CM start date as the imputed CM end date.

Impute CM start date:

1. If the CM start date year value is missing, the imputed CM start date is set to one day prior to treatment start date.
2. If the CM start date year value is less than the treatment start date year value, the CM started before treatment. Therefore:
 - a. If the CM month is missing, the imputed CM start date is set to the mid-year point (01JulYYYY).
 - b. Else if the CM month is not missing, the imputed CM start date is set to the mid-month point (15MONYYYY).
3. If the CM start date year value is greater than the treatment start date year value, the CM started after treatment. Therefore:
 - a. If the CM month is missing, the imputed CM start date is set to the year start point (01JanYYYY).
 - b. Else if the CM month is not missing, the imputed CM start date is set to the month start point (01MONYYYY).
4. If the CM start date year value is equal to the treatment start date year value:

- a. And the CM month is missing or the CM month is equal to the treatment start date month, then the imputed CM start date is set to one day prior treatment start date.
- b. Else if the CM month is less than the treatment start date month, the imputed CM start date is set to the mid-month point (15MONYYYY).
- c. Else if the CM month is greater than the treatment start date month, the imputed CM start date is set to the month start point (01MONYYYY).

If complete (imputed) CM end date is available and the imputed CM start date is greater than the (imputed) CM end date, then imputed CM start date should be set to the (imputed) CM end date. **Concomitant Medication Date Flag**

If not a complete date then

Y - If year of the imputed date is not equal to YYYY else M – If month of the imputed date is not equal to MON else D.

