5.5.6 Rescue medication

Rescue treatment will not be allowed during the first 52 weeks. Mild to moderate potency glucocorticosteroids will be permitted during the Follow-up Epoch.

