- **Arm B1:** Subjects with new-onset plaque psoriasis will receive either 1 or 2 cycles of nb-UVB of 12 weeks each with a maximum break of 28 weeks between cycles (subjects with PASI 90 at Week 40 will not receive a second treatment cycle). Only during the first 4 weeks of each cycle, nb-UVB treatment will be given in combination with topical calcipotriol 50 µg/g and betamethasone 0.5 mg/g.

Follow-up Phase

At the end of the Treatment Phase at Week 52, all subjects with \geq PASI 50 response from Arm A1 and Arm B1 will enter the Follow-up Phase. Subjects who do not achieve a PASI 50 response, will have all assessments of end of study (EOS) and be discontinued from the study.

[figure not shown]
During the Follow-up Phase, subjects will not receive study treatment; they will be observed maximally until Week 208, and compared regarding the proportion of them who achieve PASI 90 response at Week 104.

Subjects who relapse (those who experience a loss of 50% of the maximum improvement in PASI score achieved during the Treatment Phase) will have all assessments of EOS and be discontinued from the study.

If no relapse occurs, subjects who achieve $<$ PASI 90 at Week 52 in Arms A1 (A1a and A1b) and B1 (B1a and B1b) will be followed until Week 104, while subjects who achieve \geq PASI 90 at Week 52 will be followed until Week 208.

The investigator should provide ongoing adequate care for subjects who relapse. If the investigator decides to continue treating the subjects with secukinumab, a new loading dose of commercially available secukinumab could be considered. The treatment with secukinumab after relapse will be out of scope of the study.

Figure 1-1 Study design – Main study

BL = baseline, EOS = end of study, KSE = key secondary endpoint, nb-UVB=narrow-band ultraviolet B, PASI = psoriasis area and severity index, PE = primary endpoint, R = randomization.

Mechanistic Sub-study

A separate informed consent will be obtained from study subjects who agree on having skin biopsies taken and therefore become eligible for this Mechanistic Sub-study. Besides the biopsies, subjects will undergo the same assessments as in the Main Study.

Treatment Phase

At the Baseline Visit, eligible subjects will be allocated to one of the treatment arms of the mechanistic Sub-study (see [Figure 1-1](#)):

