2.4.2 Prior and concomitant medications

Prior treatments are defined as treatments taken and stopped prior to the first dose of study treatment.

Any treatment given at least once between the day of first dose of randomized study treatment (Baseline) and 84 days after the last dose of study treatment or last visit (including follow-up visits) will be a concomitant treatment, including those which were started pre-Baseline and continued into the Treatment Phase.

Concomitant medications and prior medications taken within the 6 months preceding study enrollment will be captured at the Screening visit, and updated at Baseline, with ongoing or not ongoing information. Prior or concomitant medication will be identified based on recorded or imputed start and end dates of medication taken. Further rules are given in section 5.3.3.

Prior and concomitant treatments will be summarized by treatment arms in separate tables for the SAF and for the Treatment Phase and follow-up period, separately. Treatments will be presented in alphabetical order, by ATC codes and grouped by anatomical main group (the 1st level of the ATC codes). Tables will also show the overall number and percentage of subjects receiving at least one treatment of a particular ATC code and at least one treatment in a particular anatomical main group.

In addition, previous psoriasis therapy

- any “previous < biologic systemic /non-biologic systemic> therapy” (yes/no)
- previous biologic systemic therapy (yes/no, with embedded subgroup “Failure”* – yes/no),
- previous non biologic systemic therapy (yes/no, with embedded subgroup “Failure”* – yes/no),
- Previous topical (yes/no), previous phototherapy (yes/no), previous photochemotherapy (yes/no) and
- “Failure to at least 2 previous psoriasis therapy (biologic systemic, non-biologic systemic, topical, phototherapy and photochemotherapy)” (yes/no will also be summarized in a similar manner.

(* at least one therapy with lack of primary efficacy or lack of secondary efficacy or lack of tolerability).

In addition, medical procedures and significant non-drug therapies as coded in MedDRA will be summarized. “Surgical and Medical Procedures” eCRF page will be used to get this information. Concomitant Medications - Topical Corticosteroid will also be summarized similarly. Concomitant Medications - Topical Corticosteroid eCRF page will be used to get this information.

Previous psoriasis therapy will be available for chronic subjects only.

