5.3.3.2 Post therapies date imputation

Same as section [5.3.3](#).

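### Capping partial concomitant-medication end dates at treatment end conflicts with the SAP's separate follow-up medication tables

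*SAP*

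**What the plan says.** SAP 5.3.3 gives three rules for a partial concomitant-medication (CM) end date.

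- Rule 1, day missing: "impute CM day as the minimum of treatment end date and the last day of the month".
- Rule 2, day and month missing: the same, with 31 December of the recorded year in place of the month end.
- Rule 3: "If imputed CM end date is less than the CM start date, use the CM start date as the imputed CM end date".

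The start-date rules follow. They close by saying that, where an imputed start falls after the end date, the "imputed CM start date should be set to the (imputed) CM end date". SAP 5.3.3.2 handles post therapies by cross-reference ("Same as section" 5.3.3). No rule makes an exception for medication taken in follow-up.

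SAP 2.4.2 tabulates prior and concomitant treatments by arm "in separate tables for the SAF and for the Treatment Phase and follow-up period, separately", and topical corticosteroids in the same manner. It separates prior from concomitant use with recorded or imputed dates, and its concomitant window extends to follow-up visits. Of follow-up, SAP 1.1 says: "During the Follow-up Phase, subjects will not receive study treatment". Protocol 5.5.6 adds: "Mild to moderate potency glucocorticosteroids will be permitted during the Follow-up Epoch".

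**The concern.** Follow-up begins after study treatment has stopped, so a cap at treatment end overrides every partial end date that belongs to follow-up, even where the site recorded month and year. The imputed date can then contradict the recorded month. Topical steroids are allowed in follow-up, so such records are to be expected.

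What is at stake is descriptive. Week 104 PASI 90 is assessed off study treatment, and the follow-up steroid table is where a reader would look to see how much other treatment accompanied the responses. A date rule that removes courses from that table makes follow-up look freer of treatment than the data show.

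**Working it through.** The documents give no figure for this point, so there is none to reproduce. The check applies the 5.3.3 rules literally to test records.

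**Inputs from the documents**
- Arm A1: last secukinumab dose at Week 48 (SAP 1.1).
- Arm B1: one nb-UVB cycle ends at about Week 12; two cycles end at the latest at about Week 12 + 28 + 12 = 52 (SAP 1.1). Patients with PASI 90 at Week 40 have no second cycle, so single-cycle patients exist by design.
- Follow-up starts after Week 52 in both arms (SAP 1.1).

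**Illustrative assumptions.** First dose on 15 Jan 2019, which puts Week 12 at 9 Apr 2019, Week 48 at 17 Dec 2019 and Week 52 at 14 Jan 2020. Treatment end date is first read as last dose. The comparison cap is a last visit at Week 104 (12 Jan 2021).

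**Formulas.** Imputed end = min(cap, end of recorded month). If end < a known start, end := start. If imputed start > imputed end, start := end. Days = end − start + 1.

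| Record | A1, cap Week 48 | B1 one cycle, cap Week 12 | B1 two cycles, cap Week 52 | Last-visit cap |
|---|---|---|---|---|
| (a) Start 10 Mar 2020, end Jun 2020 | 1 day, 10 Mar 2020 | 1 day, 10 Mar 2020 | 1 day, 10 Mar 2020 | 113 days |
| (b) Start Mar 2020, end Jun 2020 (both partial), listed order | 1 day, 17 Dec 2019 | 1 day, 9 Apr 2019 | 1 day, 14 Jan 2020 | 122 days |
| (c) Start 15 Oct 2019, end Jun 2020 | 64 days, to 17 Dec 2019 | 1 day, 15 Oct 2019 | 92 days, to 14 Jan 2020 | 260 days |
| (d) Start 10 May 2019, end Aug 2019 | 114 days | 1 day, 10 May 2019 | 114 days | 114 days |

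**Reading the rows**
- (a) lies wholly in follow-up with a known start. The capped end precedes the start, so rule 3 sets end to start. The record stays in follow-up but its end date is wrong.
- (b) has no complete start when the end date is imputed, so the end goes to the cap. The start is then imputed as 1 Mar 2020, found to be later than the end, and pulled back to it. The record leaves follow-up. If the start is imputed first, rule 3 gives one day on 1 Mar 2020, still in follow-up. The result depends on the order of execution.
- (c) spans both periods. Its end falls at or before Week 52 under every cap, so it no longer overlaps follow-up.
- (d) lies wholly in the treatment phase. Here alone the result differs by arm with no follow-up use involved. The gap between the A1 and single-cycle B1 caps is 48 − 12 = 36 weeks.

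**What treatment end date means.** SAP 5.3.3 does not define it. SAP 2.15.3 uses it in the formula for the time from last dose to Week 52, so there it means last dose. If it meant the end of the treatment phase, both arms would be capped at Week 52: the arm difference in (c) and (d) would vanish, while the follow-up losses in (a) to (c) would remain.

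**The case against.** Several objections narrow the point, and most of them stand.

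- A reader might infer that follow-up steroid use is under-recorded differently by arm. It is not. Caps at Week 12, 48 or 52 all fall at or before the start of follow-up, and rows (a) to (c) lose the same follow-up use under each.
- A reader might take 40 weeks (52 − 12) as the imbalance. That compares single-cycle B1 with the phase end; the A1 cap, on the same reading, is Week 48, so the contrast is 36 weeks. It concerns treatment-phase dates only and rests on treatment end date meaning last dose. Elsewhere the SAP works with the end of the treatment period or phase (2.5.4, 2.8, 5.3.1).
- The fall from 113 days to 1 is the most striking number but changes no visible planned count. SAP 2.4.2 reports numbers and percentages of subjects with at least one treatment, and row (a) still counts. No summary of CM duration appears in the readable text.
- SAP 2.4.2 does not say how a course spanning both periods is assigned. If by start date, row (c) would not enter the follow-up table whatever its end date.
- The cap has a use: it stops a course that ended during treatment from spilling into follow-up through a month-end or year-end imputation.

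None of this rescues the rule for follow-up records. A treatment-end cap cannot give a correct end date for a course that ended later, and applying it to post therapies makes the mismatch plain.

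**Conclusion.** The cap in end-date rules 1 and 2 is inconsistent with the follow-up medication and topical-corticosteroid tables in SAP 2.4.2. Two kinds of record can be lost from those tables: courses spanning treatment and follow-up with a partial end date, if tables are built by overlap; and follow-up courses with both dates partial, if the rules run in listed order. A third kind, with a complete follow-up start date, is counted but carries a wrong end date.

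The point is minor. Only partial end dates are affected, and the documents do not say how many there are. It would be tempting to conclude that the Week 104 comparison is biased. The documents do not support that: no response or missing-data rule for the primary or key secondary endpoint (SAP 2.5 and 2.6) uses CM dates. The effect is confined to medication summaries and listings.

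**What to change.** In SAP 5.3.3, end-date rules 1 and 2, replace treatment end date with last study visit date (EOS); 5.3.3.2 inherits the change. In SAP 2.4.2, state that a medication enters the follow-up table if its recorded or imputed dates overlap follow-up. With the last-visit cap, rows (a), (b) and (c) all fall in follow-up, and row (d) gives 114 days in every arm.

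The cost is a short SAP edit and one change to the derivation; the last visit date is already used in the adverse-event rule (SAP 5.3.2). One side effect should be accepted knowingly: some treatment-phase courses will be carried into follow-up. In the example, an end date of January 2020 with the day missing becomes 31 January, 17 days after Week 52. The existing imputation flag lets such records be identified in the listings.

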5.3.3.1 Prior therapies date imputation

Same as section [5.3.3](#).

5.3.3.2 Post therapies date imputation

Same as section [5.3.3](#).

5.3.3.3 First diagnosis date imputation

1. If the first diagnosis day/ month are missing and the year is non-missing:

- a. If the year part of the first diagnosis date is equal to the year part of the inform consent date, then the imputed first diagnosis date is set to the year start point (01JanYYYY).
- b. Otherwise the imputed first diagnosis date is set to the mid-year point (01JulYYYY).

2. If the first diagnosis day is missing and the month/year are non-missing:

- a. If the month and year part of the first diagnosis date is equal to the month and year part of the inform consent date, then the imputed first diagnosis date is set to the month start point (01MONYYYY).
- b. Otherwise the imputed first diagnosis date is set to the mid-month point (15MONYYYY).

5.4 AEs coding/grading

Adverse events will be coded according to MedDRA dictionary. The MedDRA version used for reporting adverse events will be described in a footnote.

5.5 Laboratory parameters derivations

Not Applicable.

5.6 Statistical models

5.6.1 Primary analysis

For the primary analysis (at Week 52), the following hypothesis testing will be performed:

$$H_{01}: p_{sec} = p_{nbUVB} \text{ versus } H_{A1}: p_{sec} > p_{nbUVB}$$

where p_{sec} and p_{nbUVB} are the proportion of PASI 90 responders in the secukinumab 300 mg s.c. (Arm A1) and nb-UVB (Arm B) groups, respectively.

Model:

Forward selection method will be performed in order to select the subset of significant covariates from Baseline PASI score, age and BMI, and their interaction with treatment.

$\text{Logit}(\pi_i) = \beta_1 * \text{treatment} + \beta_2 * \text{Baseline PASI score} + \beta_3 * \text{age} + \beta_4 * \text{BMI} + \beta_5 * \text{Baseline PASI score} * \text{treatment} + \beta_6 * \text{age} * \text{treatment} + \beta_7 * \text{BMI} * \text{treatment} + \text{error}$

where π_i is the probability that the i th subject is PASI 90 responder given that i th subject receives x_j treatment, where treatment x_j is AIN if j is 1 and nb-UVB if j is 2.

SAS code:

Using the PROC LOGISTIC the estimates of treatment differences and corresponding adjusted odds ratio and 95% CI. For Primary , Additional secondary objective. And in Other section as applicable.

```
proc logistic data= <PASI_IGA> descending covout outest=betas;
  class TRT/param=glm;
  model RESPONDER (event='1')= <Baseline XXX> <Treatment> <Age> <BMI>
    / selection=forward

    details
    lackfit;
  lsmeans trt/diff cl exp ODDSRATIO;
ods output diffs=lsm_diff;
run;
```

If there is any convergence issues, then

For Non convergence, Wald test:

```
PROC FREQ DATA=<Imputed dataset> ORDER=DATA;
  Weight <Count>;
```

```
TABLES <treatment group>*<response variable>/riskdiff(equal var=NULL CI=wald) alpha=0.05;  
RUN;
```

Multiple Imputation

The number of imputations will be set to 500, the seed for the random function will be set to 4572322. The input data set should have one record per subject with Baseline PASI score as well as all change from Baseline PASI score.

To generate the multiple imputed data sets proc MI can be used as follows (example):

```
ODS LISTING CLOSE;  
ODS OUTPUT MissPattern=msgpat VarianceInfo=varinfo ParameterEstimates=param;  
PROC MI DATA=<pasi> OUT=<impdata> SEED=457<studycode> NIMPUTE=500;  
VAR <Baseline BMI> <age>  
    <Baseline PASI>  
    <change from baseline PASI week 16> - <change from baseline PASI week 52> PASI week primary endpoint  
BY <treatment group>;  
RUN;  
ODS LISTING;
```

Programming notes:

- The SAS procedure MIANALYZE expects a variable called “_IMPUTATION_” which is generated by the MI procedure. It might be needed to set the SAS option “VALIDVARNAM=UPCASE” temporarily in the program before the MI call, this option should be reset after the MIANALYZE call to VALIDVARNAM=V6.
- In case there are none missing in one treatment group, the MI procedure does not impute any values. In this case the corresponding data need to be imputed manually outside PROC MI and added to the dataset <impdata>.

The imputed data are saved in data set <impdata>. The outcomes of interest, i.e. the PASI 90 response will be calculated, e.g. as follows:

```
DATA <impdata2>;  
SET <impdata>;  
IF <change from Baseline PASI week primary endpoint>/<Baseline PASI <= -0.90 THEN <PASI 90 response> =1;  
ELSE <PASI 90 response>=0;
```

The treatment differences for each imputed data set will then be evaluated by means of a logistic regression model with treatment as an explanatory variable and significant covariates among Baseline PASI score, age, and BMI, and interaction terms with treatment as covariates, as described in [Section 2.5.2](#).

This analysis will be done by `_IMPUTATION_` for each pairwise comparison to the nb -UVB group. The data set should be sorted such that the nb-UVB group comes last. The model should be estimating response probability = 1 by using `DESECCENDING` option.

The `MIANALYZE` procedure expects the parameter estimate in the variables `ESTIMATE`, and the corresponding standard error in the variable `STDERR`. The standard error can be derived for the log(odds ratio). Based on the data set `Common RelRisks`, as described above, those can be programmed as

```
...  
IF value NE . AND value>0 THEN ESTIMATE=LOG(value);  
IF lowercl NE . AND value>0 THEN STDERR=LOG(lowercl/value)/-PROBIT(1-<alpha>/2);  
Effect="LogOR";  
...
```

The estimates and standard errors of the log(odds ratio) based on the 500 imputed data are then combined by applying Rubin's rules for multiple imputed data sets, see Little and Rubin (2002).

Programming notes:

- The variables `ESTIMATE` and `STDERR` in the input data set for the `MIANALYZE` procedure may not be missing. Records with missing values need to be deleted and the variable `_IMPUTATION_` needs to be renumbered and regenerated since for each bygroup the procedure expects consecutive numbers starting at 1.
- The `ESTIMATE` and `STDERR` in terms of odds ratios from logistic regressions will be transformed to follow a normal distribution before `MIANALYZE` procedure. They will be transformed back to Odds Ratio to get the corrected `ESTIMATE` and corresponding CIs.

An example SAS procedure `MIANALYZE` will be applied as follows:

```
DATA <modified dataset_t>;  
SET <modified dataset>;  
stderr= stderr;  
VARIABLE="estimate";  
RUN ;  
  
ODS LISTING CLOSE;  
ODS OUTPUT ParameterEstimates=<results> VarianceInfo=<varinfo> ModelInfo=<modelinfo>;  
PROC MIANALYZE PARMS=<modified dataset>;  
BY <by-variables>;  
MODELEFFECTS ESTIMATE;  
RUN;  
  
ODS LISTING;  
data <results_back>;  
set <results>;  
estimate=exp(ESTIMATE);  
LCLMEAN=estimate*exp(-1.96*stderr);  
UCLMEAN=estimate*exp(+1.96*stderr);  
RUN ;
```

The ODS OUTPUT data set ParameterEstimates contains the estimate for the log(odds ratio), in ParameterEstimates.Estimates and the lower and upper confidence intervals (ParameterEstimates.LCLmean and ParameterEstimates.UCLmean). These three variables can be back-transformed and will be displayed together with the variable ParameterEstimates.PROBT. For the statistical appendix the ODS OUTPUT data sets Parameter Estimates, VarianceInfo and ModelInfo will be merged and displayed.

Result displayed:

Estimated adjusted odds ratio and the associated 95% confidence interval long with p-value.

In case if logistic regression does not converge, risk difference estimates will be provided. The SAS procedure PROC FREQ for risk difference estimates will be applied as follows:

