2.5.2 Statistical hypothesis, model, and method of analysis

For the primary analysis, the following hypothesis testing will be performed:

$$H_{01}: p_{sec} = p_{nbUVB} \text{ versus } H_{A1}: p_{sec} > p_{nbUVB}$$

where p_{sec} and p_{nbUVB} are the proportion of PASI 90 responders in the secukinumab 300 mg s.c. (Arm A1) and nb-UVB (Arm B1) groups, respectively.

The primary analysis method for PASI 90 response at Week 52 will use a logistic regression model with treatment as an explanatory variable and significant covariates among Baseline PASI score, age, and BMI. The best subset of the significant covariates will be selected using a forward selection method based on the likelihood ratio test. Interaction terms with treatment will also be considered, if significant, among the best subset of selected covariates and the treatment term.

Statistical significance will be evaluated at a 1-sided alpha level of 0.025. The estimated adjusted odds ratio for Arm A1 versus Arm B1 will be displayed along with the associated 2-sided 95% confidence interval (equivalent to the 1-sided 97.5% confidence interval) and p-value.

If there are issues related to the convergence of the logistic regression model, the above hypothesis will be tested using a 1- sided Wald test.

The primary analysis is not expected to be influenced by the use of topical treatment within the first 4 weeks since, any effect will be worn off by Week 52.

The detailed testing strategy including the primary endpoint analysis is provided in Section [2.6.2](#)

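### The SAP 5.6.1 code template lets forward selection drop treatment from the primary model, although the SAP text always keeps it in

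*SAP*

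**What the plan says.** SAP 2.5.2 defines the primary analysis of PASI 90 at Week 52 as "a logistic regression model with treatment as an explanatory variable and significant covariates among Baseline PASI score, age, and BMI". The covariates are chosen by a "forward selection method based on the likelihood ratio test. Interaction terms with treatment will also be considered". The Model paragraph of SAP 5.6.1 describes the selection step in the same way: "select the subset of significant covariates from Baseline PASI score, age and BMI, and their interaction with treatment". Its model equation includes a treatment term. The multiple imputation text in 5.6.1 repeats it: "The treatment differences for each imputed data set will then be evaluated by means of a logistic regression model with treatment as an explanatory variable".

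The PROC LOGISTIC template in SAP 5.6.1 is offered for the primary and additional secondary objectives, and for other sections where applicable. Its model line is "model RESPONDER (event='1')= <Baseline XXX> <Treatment> <Age> <BMI>", followed by `selection=forward` and the options `details` and `lackfit`. It then requests least-squares means for treatment and writes "ods output diffs=lsm_diff".

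For pooling, 5.6.1 says the standard error "can be derived for the log(odds ratio). Based on the data set" named `Common RelRisks`, and calls that data set described above. A programming note tells the user to delete records whose estimate or standard error is missing and to renumber the imputations. The text also says the estimates "based on the 500 imputed data are then combined by applying" Rubin's rules.

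**The concern.** In the text, treatment is fixed and only covariates and interactions are candidates. In the code, treatment is one of four candidates and the interactions are absent. The likelihood ratio criterion of 2.5.2 and the entry level are not stated either. A programmer who follows the template gets a model that can leave out the effect under test and then asks for a treatment contrast from it.

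The hand-off to the pooling step is also unclear. The template writes `lsm_diff`, the pooling text reads `Common RelRisks`, which no printed step creates, and a later note says the odds ratios come from logistic regressions.

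This is the test that opens the gate to the Week 104 hypothesis (SAP 2.6.2). Suppose the template were run by imputation and sets without a treatment estimate were then deleted. Rubin's rules would pool only those sets in which treatment had already passed a significance test. That would bias the odds ratio away from 1 and could inflate the type I error.

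**Working it through.** **Text against code**

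| Feature | SAP 2.5.2 and 5.6.1 text | 5.6.1 template |
|---|---|---|
| Treatment | always in the model | candidate, nothing forces it in |
| Treatment interactions | candidates | not listed |
| Selection criterion | likelihood ratio test | not stated |
| Entry level | not stated | not stated |
| Source of pooled estimate | `Common RelRisks`; elsewhere logistic regression | `lsm_diff` |

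This comparison establishes the contradiction. It assumes the usual behaviour of forward selection: a listed effect that is not forced in is a candidate.

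**The plan's own figure.** SAP 3 gives 80 per arm, 70% v 28%, one-sided 0.025 and 99.9% power.
- Unpooled SE = √[(0.70×0.30 + 0.28×0.72)/80] = 0.0717. Power = Φ(0.42/0.0717 − 1.96) = 99.995%.
- Pooled SE under the null = √[2×0.49×0.51/80] = 0.0790. Power = Φ[(0.42 − 1.96×0.0790)/0.0717] = 99.99%.

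The stated power is reproduced and is not in dispute.

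**How often treatment would fail to enter one complete data set.** Assume entry at 0.05 by the score test with no covariates: enter if (p₁ − p₂)² / [2p̄(1 − p̄)/80] > 3.84. Exact binomial enumeration gives these probabilities of not entering:
- 70% v 28%: 0.02%
- 70% v 35%: 0.5%
- 50% v 35%: 53%
- equal rates: about 95%

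At 50% v 35% the true odds ratio is (0.50×0.65)/(0.50×0.35) = 1.86. The mean odds ratio given entry is 2.44.

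**What pooling only the surviving sets does.** Each retained set already has |z| above about 1.96, so the pooled estimate tends to be significant too. For the k sets kept, Rubin's variance is T = W̄ + (1 + 1/k)B, and H01 is rejected at one-sided p < 0.025.

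The simulations used 80 per arm, 500 imputations and a true null (35% or 50% in both arms). Ranges span two models:
- a covariate-free model with binomial imputation by arm (6,000 null trials per scenario);
- a model with correlated PASI visits, BMI related to response, monotone dropout and normal imputation by arm (3,000 null trials per scenario).

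Monte Carlo SE is at most 0.75 points under the null. One-sided type I error (%) at entry 0.05:

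| Missing for other reasons | Pool any 2+ sets | Need ≥50 sets | Need ≥250 sets | Treatment forced in, all 500 |
|---|---|---|---|---|
| 2.5% | 4.5–5.3 | 3.5–4.2 | 2.0–2.8 | 1.9–2.5 |
| 5% | 7.4–8.3 | 4.4–5.6 | 2.4–3.1 | 1.9–2.6 |
| 10% | 11.2–14.4 | 5.5–7.3 | 2.1–3.5 | 1.7–2.6 |
| 20% | 21.1–28.7 | 7.3–12.3 | 1.6–4.0 | 1.1–2.6 |

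With nothing missing, the error is 2.4–2.5%. Pooling any 2+ sets at 2.5/5/10/20% missing gives:
- entry 0.10: 2.0–2.7, 2.2–3.1, 2.4–3.7 and 3.1–7.5%;
- entry 0.20: 1.9–2.5, 1.9–2.6, 1.7–2.7 and 1.3–3.1%.

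A simpler covariate-free run (4,000 trials, 35% v 35%, pooling even a single surviving set) gave 8.6, 16.0 and 30.4% at 5, 10 and 20% missing, against 2.6, 2.5 and 2.1% with treatment forced in. In 82, 67 and 36% of those trials no set carried a treatment estimate, so nothing could be pooled.

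**With a true effect.** At 50% v 35% and 10% missing, pooling 2+ sets:

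| Entry level | Pooled OR | Rejection |
|---|---|---|
| 0.05 | 2.32 | 73–77% |
| 0.10 | 2.15–2.18 | 47–52% |
| 0.20 | 2.02–2.04 | 41–45% |
| Treatment forced in | 1.84–1.87 | 40–44% |

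If all 500 sets must carry an estimate, rejection at entry 0.05 falls to 15–16%.

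At 70% v 28% and 10–20% missing, 0.0–0.3% of sets are lost, the odds ratio is unchanged, and H01 is rejected in 99.8–100% of trials either way.

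**The case against.** The governing text is clear. Protocol 9.4.2, SAP 2.5.2, the 5.6.1 model equation and the imputation text all keep treatment in. SAP 2.6.2 keeps it for the key secondary endpoint even when no covariate is significant. The template is a shared skeleton with placeholders and no BY statement, so a programmer has to adapt it anyway. The delete-and-renumber note follows code that screens for undefined odds ratios, so unselected treatment is probably not its target. The text also speaks of combining all 500 imputed data sets.

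The high error rates need a chain of assumptions, and the highest need 20% missing for other reasons and pooling of very few sets. The 20% dropout in SAP 3 is for Arm B1 only and is counted as non-response, so it is not imputed. If all 500 sets had to carry an estimate, the template would be conservative, with null rejection of 0.1–1.1%. Losing most of the sets would also be hard to miss. Finally, some code in 5.6.1 is announced but not printed, so an option could have been lost.

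Much of this stands as a limit on size. It does not remove the conflict. The template is the only code printed for the primary model, the SAP assigns it to that analysis, and 5.6.1 says the analysis is done by imputation. The code block runs through to its closing `run;`, so a lost option is speculation. SAP 2.13.4, on IGA at Week 104, expects that with a non-significant treatment difference nothing may be selected, and it plans a Wald test. That hints that treatment may have gone through selection in practice, although it does not govern the primary analysis. For H01 the only fallback is for non-convergence.

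**Conclusion.** The concern holds. The printed code contradicts the SAP text on whether treatment is subject to selection, for the test that gates the Week 104 hypothesis. It should be fixed.

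Under the planned effect the consequence is nil. Away from it, the level of H01 is at risk only if three things coincide: the template is run by imputation, sets without a treatment estimate are dropped, and the entry level is near 0.05 (or 0.10 with heavy missingness). The size then depends on how few surviving sets are accepted for pooling. The documents give no entry level, no rate of missingness for other reasons and no minimum number of sets, so the error rates are conditional illustrations. Whether an unselected treatment leaves a missing record or no record at all depends on the software.

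The three-covariate sensitivity model in SAP 2.5.4 has no selection and would expose a discrepancy, but it does not gate H02. For IGA at Week 52 missing responses are set to non-response, so nothing is pooled there. The template could still return no treatment estimate.

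**What to change.** In SAP 5.6.1:

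1. List treatment first in the MODEL statement with `INCLUDE=1`, so that only covariates and interactions are selected. The order matters, because the template now lists treatment second.
2. Add the treatment interactions of 2.5.2 as candidates, and state at which covariate value the odds ratio is taken if one enters.
3. Apply the likelihood ratio criterion of 2.5.2 and state the entry level.
4. Name the logistic regression output (`lsm_diff`) as the input to MIANALYZE, in place of `Common RelRisks`.
5. Limit the delete-and-renumber note to fits that fail to converge, and report how many of the 500 sets were pooled.
6. SAP 2.14.1 says a Week 52 report was prepared, so confirm which code was run. Rerun with treatment forced in if it was the printed template.

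Use the corrected code for IGA as well. Optionally, use one covariate set across all imputations so that the pooled odds ratio has a single definition; this does not affect the level.

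The cost is a few lines of code and SAP wording, with no new data or patients. Likelihood ratio entry may need a short macro. If a rerun changes a Week 52 figure, the study report must explain it.
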